the clinical staff. Patients/caretakers will return all empty syringes and vials to the clinic when they visit (the number recorded) and both clinic administered study drug, as well as outpatient study drug administration will be recorded by the patient in a study diary.

- 13 Injection site evaluations and scoring (by the clinical staff) will include identification and measurement of areas of erythema, edema and induration, as well as the presence of localized pain, tenderness and itching. Additional evaluation data can be collected at any visit where there are injection site reactions even if not a timepoint for formal assessment.
- 14 All BP and HR measurements are to be obtained in the sitting position following at least 5 minutes of rest. All measurements will be taken in triplicate, approximately 2 minutes apart. On Day 1 and Day 14, patients will have vitals obtained pre-dose. When possible, BP should be taken in the same arm throughout the study, using the same methodology (automated or manual). Body temperature (°C) and respiration rate (breaths/minute) will be obtained in the sitting position following at least 5 minutes of rest.
- 15 On Treatment Day 15, at the end of the single-blind placebo run-in but prior to beginning dosing in the 4 week double blind treatment period.
- 16 A single 12-lead ECG will be performed in the supine position following a period of at least 10 minutes of rest, at Screening, on Day 42 and at poststudy.
- 17 Safety laboratories to be collected at screening. Safety laboratories also to be collected on Day 15, 28 (if clinic visit occurs) 42, Day 70 and at Poststudy. CBC with platelet count and standard indices, chemistry panel (includes sodium, potassium, chloride, CO₂, albumin, total protein, glucose, BUN, creatinine, uric acid, AST, ALT, GGT, CPK, alkaline phosphatase, total bilirubin, direct bilirubin, LDH, calcium, phosphorus), urinalysis with microscopic analysis if positive findings on dipsticks warrant further examination. Fasting samples (8 hr minimum) are required at all timepoints where feasible in this population

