6.4.6. Vital Signs

Vital signs will be obtained in the sitting position following at least 5 minutes of rest each time they are measured, at the times outlined in the SOA.

Blood pressure and heart rate

Blood pressure (BP; mmHg) and heart rate (HR; bpm) are to be measured according to the SOA. At each timepoint, BP and HR measurements will be performed *in triplicate approximately 2*

minutes apart, using the same methodology throughout the study (manual or automated). Careful attention should be paid to using an appropriately sized BP cuff.

When possible, BP should be taken in the same arm throughout the entire study period.

Repeat measures and more frequent monitoring can be implemented for significant increases in BP or HR.

Body temperature and respiration rate

Body temperature (°C) and respiration rate (breaths/minute) will be obtained in the sitting position following at least 5 minutes of rest according to the SOA.

6.4.7. 12-Lead Electrocardiogram

Single 12-lead electrocardiograms will be performed following a period of at least 10 minutes of rest in the supine position according to the SOA.

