6.4.9. Injection Site Evaluation and Scoring

Injection sites will be carefully inspected, evaluated and scored during the study period. The injection site evaluation will include identification and measurement of areas of erythema, edema and induration, as well as the presence of localized pain, tenderness and itching. A sample injection site evaluation form is included in the [Appendix](#).

Injection site evaluations and scoring will be conducted according to the SOA. In addition, unscheduled evaluations may also be recorded as warranted by clinical conditions.

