For both serious and non-serious adverse events, the Investigator must determine both the intensity of the event and the relationship of the event to study drug administration. Only those injection site reactions considered clinically significant by the Investigator will be recorded as AEs.

Intensity of all AEs including clinically significant treatment-emergent laboratory abnormalities, injection site reactions and potential systemic reactions will be graded according to the CTCAE Version 4.0. The CTCAE grade refers to the severity of the AE and ranges from Grade 1 (mild AE), Grade 2 (moderate AE), Grade 3 (severe AE) and Grade 4 (life-threatening or disabling AE) to Grade 5 (death related to AE).

Adverse events not listed by the CTCAE will be graded as follows:

Mild: discomfort noticed but no disruption of normal daily activity.

Moderate: discomfort sufficient to reduce or affect daily activity.

Severe: inability to work or perform normal daily activity.

Life threatening: represents an immediate threat to life.

Relationship to study drug administration will be determined by the investigator according to the following criteria.

None: No relationship between the event and the administration of study drug. The event is related to other etiologies, such as concomitant medications or patient's clinical state.

Unlikely: The current state of knowledge indicates that a relationship to study drug is unlikely or the temporal relationship is such that study drug would not have had any reasonable association with the observed event.

Possible: A reaction that follows a plausible temporal sequence from administration of the study drug and follows a known response pattern to the suspected study drug. The reaction might have been produced by the patient's clinical state or other modes of therapy administered to the patient.

Probable: A reaction that follows a plausible temporal sequence from administration of the study drug and follows a known response pattern to the suspected study drug. The reaction cannot be reasonably explained by the known characteristics of the patient's clinical state or other modes of therapy administered to the patient.

For the purpose of safety analyses, all AEs that are classified as possible or probable will be considered treatment-related events.

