11.10. Evaluation of Abnormal Liver Function Tests (LFTs)

While there has been no signal of elevated LFTs during the Phase 1/2 studies of RM-493, nor any signal identified in the toxicological studies, the following is guidance for evaluation of any LFT abnormalities identified during the course of this study

1. If ALT or AST>3 ULN, repeat in 48-72 hrs.
2. If repeat ALT or AST are still >3 ULN, repeat LFTs (including transaminase, alkaline phosphatase and bilirubin levels) every 48-72 hrs. In addition, the following should be performed:

Obtain a detailed history of symptoms, prior and concurrent diseases, concomitant drug use (including OTC, herbal and dietary supplements), alcohol and recreational drug use and special diets

Obtain history of exposure to environmental chemical agents

Consider evaluation for acute viral hepatitis types A, B, C, D and E, autoimmune or alcoholic hepatitis, nonalcoholic steatohepatitis (NASH), biliary tract disease and ischemic liver injury

Consider additional tests to evaluate hepatic function, as appropriate, such as INR.

Consider hepatology consultation

Frequency of repeat testing can be reduced if LFT abnormalities stabilize or if the patient is asymptomatic and study drug is discontinued.

3. Discontinue study drug administration if:

ALT or AST>8xULN on any single determination

ALT or AST >5xULN for more than 2 weeks

ALT or AST >3xULN with total bilirubin >2xULN or INR >1.5

ALT or AST >3xULN with the appearance of fatigue, fever, rash, and/or eosinophilia (>5%) or nausea, vomiting, right upper quadrant pain or tenderness that is more frequent and/or more severe than patient's baseline DG symptoms

4. Follow-up to Resolution: All study patients with clinically significant treatment-emergent LFT abnormalities should be followed until values return to normal or baseline levels

Adapted from: US Department of Health and Human Services, Food and Drug Administration, Center for Drug Evaluation and Research (CDER) Center for Biologics Evaluation and Research (CBER). Guidance for Industry Drug-Induced Liver Injury: Premarketing Clinical Evaluation. [name]. July 2009.

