4.2 General Considerations

Data will be described and analyzed using the Statistical Analysis System (SAS), version 9.2 or higher on a Windows platform (SAS Institute Inc., Cary, NC). Adverse events and medical history will be coded using MedDRA Version 18.1. Prior and concomitant medications will be coded to provide Anatomical Therapeutic Chemical (ATC) levels 2 (therapeutic main groups) and 4 (chemical subgroups) using the December 2014 version of the World Health Organization (WHO) Drug Dictionary.

Individual patient data will be presented in by-patient data listings. Descriptive statistics (number of patients [n], mean, standard deviation [SD], median, minimum [Min] and maximum [Max]) will be presented for continuous data. For categorical data, the frequency and percentage of patients in each category will be presented; percentages will be based on the number of patients with non-missing observations.

Unscheduled visits will not be used, unless they meet the criteria for a baseline observation (e.g. last observation prior to initial double-blind drug administration).

A by-patient listing will be provided which includes all derived efficacy data for which the derivation is not otherwise provided. The data as collected will be provided in the relevant by-patient listing of the raw data.

Unless specified otherwise, by-patient listings will be provided for all data as contained in the raw database.

Reporting of treatment groups in summary tables will be performed with placebo groups (high and low dose groups) combined. The primary focus for the treatment group analysis will be on Period 2 (the 4-week double blind period). Additional analyses will focus on specific intervals (Period 3; effect of randomized change in treatment from active to placebo, and placebo to active); Period 4 (the open label, 1.5 mg dose 2-week active extension), and Period 1 (the double-blind, placebo controlled run-in period).

The final study analysis will include summaries from pooled data using identical active doses (e.g., 0.5 mg, 1.5 mg, 2.5 mg) across the whole study, including data from before and after any interim analysis. As mentioned above, all placebo data will be pooled as well.

Supplemental exploratory analyses will be done for Period 1 (run-in) data to help in understanding of the variability of PWS subjects in a clinical trial; this data will complement the placebo data obtained later in the trial.

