4.8 Safety Analyses

4.8.1 Adverse Events (AEs)

Adverse events are to be recorded from signing the informed consent through the Final Study Visit (~ 2 weeks post treatment). All AEs (serious and non-serious) spontaneously reported by the patient and/or in response to an open question from study personnel or revealed by observation, physical examination or other diagnostic procedures will be recorded. An adverse event is considered to be treatment-emergent if the onset date/time is during or after administration of double-blind study drug or, in the event that onset time precedes double-blind study drug administration, the adverse event increases in severity during or after administration of double-blind study drug; in either case through 1-week after the last treatment dose.

Imputations will be used for determining treatment emergence for adverse events with partial dates (see Section 4.2.2); the unimputed partial dates will be included in the data listings.

A top line summary of AE incidence will be presented by treatment group. The number and percentage of patients with any treatment-emergent AE (TEAE), with any TEAE leading to study drug discontinuation, serious TEAE, and with any AE based on an injection site assessment will be summarized by dose group and period. In addition, the TEAE and SAE tables will be analysed by AE severity.

The following AE summaries will be produced by SOC and preferred term, by period:

- Incidence of TEAEs
- Incidence of TEAEs by severity
- Incidence of SAEs
- Incidence of SAEs by severity

A frequency of injection site reactions (Erythema, Edema, Induration, Itching, Pain or Tenderness, Other) will also be produced by each period, summarized by dose group.

All AEs will be provided in a by-patient listing which will include both the term reported on the CRF (verbatim term) and the preferred term and SOC to which it is coded. Relative start and stop days will be included along with the actual onset and resolution dates and times. AEs that are not considered treatment-emergent will be provided in a separate listing.

In addition, separate listings will be provided for the following, whether or not considered to be treatment-emergent (non treatment-emergent AEs will be flagged):

- Serious adverse events (SAEs)
- Adverse events leading to death or discontinuation of study drug (treatment-emergent)

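### SAP 4.2 excludes unscheduled visits with no exception for safety, so some injection-site reactions reach no summary table, and the SAP omits safety tables that protocol 8.5 promises

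*SAP*

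**What the plan says.** The rule stands in SAP 4.2, General Considerations: "Unscheduled visits will not be used, unless they meet the criteria for a baseline observation". Nothing in SAP 4.8 brings unscheduled data back into a safety table. The same section of the SAP does keep them in listings: "Unless specified otherwise, by-patient listings will be provided for all data as contained in the raw database".

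The protocol expects safety data outside the schedule. Section 6.4.9, on injection sites, says: "In addition, unscheduled evaluations may also be recorded as warranted by clinical conditions". Footnote 13 to Table 6-1 adds: "Additional evaluation data can be collected at any visit where there are injection site reactions even if not a timepoint for formal assessment". Section 6.4.6 says of vital signs: "Repeat measures and more frequent monitoring can be implemented for significant increases in BP or HR". Section 11.10 says of liver tests: "If ALT or AST>3 ULN, repeat in 48-72 hrs".

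For reporting, SAP 4.8.1 plans: "A frequency of injection site reactions (Erythema, Edema, Induration, Itching, Pain or Tenderness, Other) will also be produced by each period". Protocol 7.2 limits which reactions also become adverse events: "Only those injection site reactions considered clinically significant by the Investigator will be recorded as AEs".

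Protocol 8.3 allows data to be left out only where a major protocol violation is involved. Protocol 8.5 promises summaries of change from baseline to any value after dosing, for vital signs and laboratory results, and a table by treatment of how many patients had abnormal safety laboratory results.

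**The concern.** Leaving unscheduled visits out is sensible for by-visit means, where an extra reading has no place. The injection-site frequency is different. It is a count by period, so an unscheduled evaluation dated in the period fits it naturally. These evaluations are made because something was seen, so the rule removes observations that are likely to be positive. The AE tables recover only the reactions judged clinically significant.

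Safety and tolerability is the first-listed primary objective, and protocol 2.2 names injection-site reactions among its measures. At stake is an undercount of local reactions in the table readers will use to compare dose groups, together with safety tables that the protocol promises and the SAP does not plan.

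**Working it through.** The plan gives no figure for this point, so the check compares texts, with a short calculation of scale.

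**1. Injection-site reactions.** For one patient in one period, let S mean that a scheduled evaluation shows a reaction, U that an unscheduled evaluation shows one, and C that a reaction is judged clinically significant.
- Counted in the SAP 4.8.1 frequency under the 4.2 rule: S.
- Counted if all evaluations were used: S or U.
- Missed by that frequency: U and not S.
- Missed by the AE tables as well: U and not S and not C.

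The last group is found only in a listing. The count under the rule can never exceed the count from all evaluations, so the error can only be an undercount. The documents do not say how often U occurs without S, so its size cannot be computed.

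**2. What one missed patient would mean.** Inputs: about 20 patients in the first half and about 16 in the second, allocated 2:1:3 (protocol synopsis; SAP 3.1), with identical doses and all placebo pooled (SAP 4.2). Assume that all randomised patients enter the Safety Set.
- Placebo: 20 × 2/6 + 16 × 2/6 = 6.67 + 5.33 = 12.0. One patient is 100/12.0 = 8.3 points.
- 0.5 mg: 20 × 1/6 = 3.33. One patient is 100/3.33 = 30 points.
- 1.5 mg: 20 × 3/6 + 16 × 1/6 = 10 + 2.67 = 12.67. One patient is 100/12.67 = 7.9 points.
- 2.5 mg: 16 × 3/6 = 8.0. One patient is 100/8.0 = 12.5 points.

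These figures show the weight of a single patient. They do not estimate how many are missed.

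**3. Against protocol 8.3.** An unscheduled visit is not a protocol violation. The SAP therefore leaves out data that the protocol keeps, and gives no reason.

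**4. Against protocol 8.5.**
- Change to any post-dose value: SAP 4.8.2 and 4.8.3 tabulate change at Day 28 and Day 42 from the Day 15 baseline. There is no any-value or worst-value table. If the protocol phrase means only each scheduled post-dose visit, the named days still end at Day 42, although the protocol schedule has safety laboratories and vital signs at Day 70 and follow-up.
- Patients with abnormal laboratory results by treatment: SAP 4.8.2 gives a listing of abnormal values, not a table.

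**5. Cause for laboratory and vital-sign data.** Because those tables name their days, a liver test repeated after 48 to 72 hours would be missing even without the 4.2 sentence. Changing 4.2 alone would not repair them. For blood pressure and heart rate, SAP 4.8.3 averages the readings at a timepoint, so repeats at a scheduled visit are included. Only those from an unscheduled visit drop out.

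**The case against.** The best case for the plan is that little is lost. All raw data go to listings, and SAP 4.8.2 adds listings of all laboratory results and of all abnormal values. It also plans laboratory plots described as covering all post-dose values through Period 2, which may take in unscheduled results. Protocol 7.2 makes clinically relevant deterioration an adverse event, so it reaches the AE tables whatever the visit type. SAP 4.8.1 also summarises patients with an AE arising from an injection-site assessment. Footnote 13 speaks of any visit, which includes scheduled ones. In a pilot of about 36 patients, listings can be read.

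Most of this stands, and it narrows the point. It does not cover reactions judged not clinically significant: protocol 6.4.9 plainly allows unscheduled evaluations of them, and a listing gives no rate by dose group. Nor does it supply the protocol 8.5 tables.

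Three stronger readings are tempting and are not supported.
- A reader might infer that repeat liver, blood pressure and heart rate readings are taken when values are highest. The protocol says only that they follow an abnormal or raised value. A repeat may be higher or lower.
- A reader might infer that most reactions are lost. For one reaction starting on a random day from Day 15 to Day 41 (27 days), a 3-day reaction is visible at Day 42 for 2/27 = 7% of start days, and at Day 28 or Day 42 for 5/27 = 19%. For a 7-day reaction the figures are 6/27 = 22% and 13/27 = 48%. The complement, 52% to 93%, is the share not visible at those inspections. It is not the share lost through 4.2, because a reaction that nobody evaluates is missed under either rule. The durations are assumed, daily dosing can cause repeated reactions, and the Day 15 inspection may come after the first double-blind dose.
- A reader might infer a known shrinkage of the drug-placebo difference. That would follow for the absolute difference if detection were equally likely in every arm. The documents give no data on this.

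**Conclusion.** The point holds in a limited form. As written, SAP 4.2 keeps one class of reaction out of every summary table: those seen only at an unscheduled evaluation, not seen at a scheduled one in that period, and not judged clinically significant. The direction is an undercount. Its size is unknown and could be zero. This rests on reading the 4.2 sentence as applying to safety, which its place under General Considerations and the lack of any exception support.

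Separately, the rule is at odds with protocol 8.3, and the SAP omits summaries that protocol 8.5 promises. The laboratory and vital-sign gap comes mainly from the named-day tables. The data are neither discarded nor hidden, so this is an inexpensive correction to make before the analysis and not a threat to the trial's conclusions.

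**What to change.** - **SAP 4.2:** limit the rule, for example: *Unscheduled visits will not be used in efficacy analyses or in by-visit summaries of safety variables, except where they qualify as baseline.*
- **SAP 4.8.1:** count a patient as having an injection-site reaction in a period if any evaluation dated in that period, scheduled or not, shows one.
- **SAP 4.8.2 and 4.8.3:** add the patient-level tables of protocol 8.5: patients with abnormal safety laboratory results by treatment, and the any or worst post-dose value for laboratory tests and vital signs, using all readings. State whether blood pressure and heart rate readings at one timepoint are averaged before the worst value is taken.

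The cost is a SAP wording change and modest programming on data already collected. The drawback is that patients with more visits have more chances of detection. Counting patients and not evaluations limits this but does not remove it, so the tables should carry a note saying so.

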4.2.1 Derived Data

The following implementations will be made for derived data:

Table 1. Derived Variables

Variable	Derivation
General	
weight (kg)	weight (lb) \times 0.454; regardless of unit, take average of weight values for any one timepoint; if only 1 value is present for a timepoint, this value will be used in the analysis
height (cm)	height (in) \times 2.54
body mass index (kg/m ²)	weight (kg) / [height (m)] ²
temperature (°C)	[temperature (°F) - 32] \times 5/9
age (yr)	integer part of (date of informed consent - date of birth) / 365.25
Study Days and Periods	
relative day, prior to treatment with study drug	date of visit - date of study drug administration [Day 1 is the day immediately prior to treatment with first study drug in the placebo controlled run-in period.]
relative day, on or after day of study drug	date of visit - date of study drug administration + 1 [Day 1 is the day treatment with DB study drug was administered.]
relative time for efficacy endpoints	date and time of the evaluation - date and time of the end of the last injection of study drug
relative time for safety evaluations	date and time of the evaluation - date and time of the start of the first injection of study drug
Baseline	See Section 4.2.5
change from baseline	See Section 4.2.5

Abbreviations: C=Centigrade, F=Fahrenheit

4.2.2 Handling of Missing Data

For a sensitivity analysis on the primary efficacy endpoints (Body Weight and PWS Hyperphagia Questionnaire), missing data from subjects who do not adhere to therapy will be imputed with the mean value from those subjects on the same arm that also did not adhere to therapy, but had the measurement for the primary endpoint.

Imputation will not be performed in the case of partial or missing dates. The relative study days, where determined, will be calculated for full dates only

Incomplete AE dates will be derived based on the following guidelines:

- The dates that are missing or incomplete are derived as follows:

If the start date/time of an AE is partially or completely missing, the date/time will be compared as far as possible with the date/time of the start of administration of study drug. The AE will be assumed to be treatment-emergent if it cannot be definitively shown that the AE did not occur or worsen during the treatment-emergent period (worst case approach).

The following general rules will be used:

- If the start time of an AE is missing but the start date is complete, an AE will only be excluded as being treatment-emergent if the start date is before the date of study drug administration or if the stop date/time is before study drug administration.

- If the start time and day are missing but the start month and year are complete, an AE will only be excluded as being treatment-emergent if the start month/year is before the month/year of study drug administration or if the stop date/time is before study drug administration.
- If the start day and month are missing but the start year is complete, an AE will only be excluded as being treatment-emergent if start year is before the year of study drug administration or if the stop date/time is before study drug administration.
- If the start date is completely missing, an AE will be considered treatment-emergent unless the stop date/time is before study drug administration.

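### The SAP 4.2.2 rules for AEs with incomplete start dates conflict with that section's own lead sentence and with the treatment-emergent definition in 4.8.1, and no order of precedence is stated

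*SAP*

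**What the plan says.** SAP 4.8.1 makes an AE treatment-emergent if it starts during or after double-blind study drug. An AE with an earlier onset qualifies if "the adverse event increases in severity during or after administration of double-blind study drug". Both routes share one upper limit: "in either case through 1-week after the last treatment dose". For incomplete dates the section points back: "Imputations will be used for determining treatment emergence for adverse events with partial dates (see Section 4.2.2").

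SAP 4.2.2 opens with a principle. An AE whose start is partly or wholly missing is assumed treatment-emergent if "it cannot be definitively shown that the AE did not occur or worsen during the treatment-emergent period (worst case approach"). The bullets then follow under the words "The following general rules will be used":

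- Time missing, date complete: "an AE will only be excluded as being treatment-emergent if the start date is before the date of study drug administration". A second ground for exclusion rests on when the event ended: "or if the stop date/time is before study drug administration".
- Day and time missing: "an AE will only be excluded as being treatment-emergent if the start month/year is before the month/year of study drug administration", with the same stop-date alternative.
- Month and day missing: the same test at the level of the year.
- Start wholly missing: only the stop-date condition remains.

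Two other places define treatment emergence. SAP Appendix 1, footnote 19, counts AEs reported after randomization, and Protocol section 7 counts AEs after the start of study drug. Neither has an upper limit. The end of AE recording is also stated in two ways. SAP 4.8.1 puts it at a final visit about 2 weeks after treatment, while the schedules in both documents mark AE assessment at the follow-up visit on Days 90 to 163.

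**The concern.** The lead sentence of 4.2.2 and its bullets give different answers for the same event. A programmer is likely to code the bullets, because they are explicit and say that an AE is excluded only under the listed conditions. Whether an event enters the treatment-emergent tables would then depend on whether someone wrote down a clock time. A missing time does not make the day uncertain, so counting an event that plainly began after the window is not a conservative choice.

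Safety and tolerability is a primary objective of the trial, and the incidence of treatment-emergent AEs is its main AE table. The arms are small, so a rule that sorts events by completeness of recording should not be left open.

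**Working it through.** The plan states no figure on this point, so there is none to reproduce. The check applies the first bullet of 4.2.2 and the definition in 4.8.1 to the same events.

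**Inputs.** Run-in dosing starts on Day 1 and double-blind dosing on Day 15 (schedules). The last dose is on Day 70, with a range of Day 68 to 74, for participants in the open-label extension (footnote 12), and about Day 56 without it. The upper limit in 4.8.1 is last dose + 7 days. I take the last treatment dose to be the last dose of study drug in any period.

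**Rules, with a complete start date and no time.**

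- Bullet: treatment-emergent unless start < reference dose or stop < reference dose.
- 4.8.1: treatment-emergent if Day 15 ≤ start ≤ last dose + 7, or if start < Day 15 and worsening falls between Day 15 and last dose + 7.

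**(a) Late side, last dose Day 70, so the limit is 70 + 7 = Day 77.**

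| Start | Bullet | 4.8.1 |
|---|---|---|
| Day 77 | emergent | emergent |
| Day 78 | emergent | not emergent |
| Day 90 | emergent | not emergent |
| Day 163 | emergent | not emergent |

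**(b) Early side.** The bullets do not say whether the reference is the Day 1 run-in dose or the Day 15 double-blind dose, so both are shown.

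| Event | Bullet, reference Day 15 | Bullet, reference Day 1 | 4.8.1 |
|---|---|---|---|
| Starts Day 10, worsens Day 20, stops Day 30 | excluded | emergent | emergent |
| Starts Day 10, no worsening | excluded | emergent | not emergent |
| Starts in screening, worsens Day 20 | excluded | excluded | emergent |

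Each reference gets some of these events wrong. The screening-onset event that worsens on drug is wrong under both.

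**Length of the exposed period, beyond last dose + 7.**

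- If AE recording ends about 14 days after treatment (4.8.1): 14 − 7 = about 7 days.
- If AEs are collected to the follow-up visit (schedules), with a Day 70 last dose: 90 − 77 = 13 days for a Day 90 visit, and 163 − 77 = 86 days for a Day 163 visit.
- For a Day 163 visit and other last doses: 163 − (68 + 7) = 88; 163 − (74 + 7) = 82; 163 − (56 + 7) = 100 days.

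**Starts known only to month and year.** These conflict with 4.8.1 only when the whole known month lies after the limit. As an illustration, assume run-in starts on 1 January 2016. Day 70 is then 10 March and the limit is 17 March. A start recorded as March 2016 could lie inside the window, so counting it is the proper worst case. A start recorded as April 2016 cannot.

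**The case against.** The strongest reply is that 4.2.2 already covers both points. Its lead sentence names worsening and the treatment-emergent period, and under it an event with a known date outside the window and no worsening inside it is definitively not emergent. The bullets are called general rules, and nothing says that they override the lead sentence. This reply stands in part. A reader might infer that the section as a whole ignores worsening and the end of the window, and it does not. But nothing says that the lead sentence prevails either, and the bullets say that exclusion occurs only under their conditions. The conflict remains.

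A second reply is that study drug, in this SAP, includes run-in placebo, so a run-in event that worsens would not be dropped. That is a fair reading, and it removes the first row of the early-side table. It also makes untimed run-in events emergent without any worsening, which 4.8.1 does not allow.

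A third reply is that the bullets agree with footnote 19 and Protocol section 7, which have no upper limit. That is true on the late side. It means that the 1-week limit is not the only definition in the documents. However, 4.8.1 is the AE analysis section, and events with complete dates and times will follow it.

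A fourth reply concerns impact. The SAP also plans SAE incidence tables, injection-site reaction tables and full listings, including non-emergent AEs. The primary safety objective concerns the 4-week double-blind period, and AE tables are by period. All of this stands. For participants who complete treatment, events more than a week after the last dose have no bearing on the Period 2 comparison.

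**Conclusion.** The point holds as an internal conflict in the SAP. The bullets of 4.2.2, read literally, classify some events differently from both their own lead sentence and 4.8.1, and the SAP does not say which governs. It merits correction before the database is locked.

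The exposed post-window period is about 7 days on the 4.8.1 statement of when AE recording ends, and up to 86 days on the schedules for a Day 70 last dose. These are calendar days, not shares of events. The documents do not say how many AEs lack a time, so the number misclassified cannot be estimated. The effect is confined to the treatment-emergent tables, and no efficacy or power figure changes.

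Three stronger readings are not supported:

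- A reader might infer that the treatment-emergent tables are the only AE summaries. The other tables and listings in 4.8.1 show otherwise.
- A reader might infer that every late AE known only to month and year is misclassified. Only those whose known month lies wholly after the limit are.
- A reader might infer that one such event shifts incidence in the randomized 2.5 mg arm by 1/8 = 12.5 points, taking 3/6 of about 16 participants. For participants who enter the extension, late events follow open-label treatment given to everyone in it, and no rule places them in that arm's Period 2 column.

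**What to change.** In SAP 4.2.2:

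1. Name the first double-blind injection as the reference dose, to match 4.8.1.
2. Classify an AE with a complete start date by date alone. An untimed AE on the day of the first double-blind injection stays emergent under the worst-case principle.
3. For a start date with at least a known year, also exclude the AE when the known part lies wholly after last dose + 7 days.
4. State that an AE with an earlier start that increased in severity on or after the first double-blind dose, within the 4.8.1 window, is treatment-emergent. This clause should take precedence over the start-date exclusion.

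Then reconcile Appendix 1 footnote 19, Protocol section 7 and the stated end of AE collection with 4.8.1, so that one definition and one collection period apply.

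For a Day 70 last dose, the latest emergent onset becomes Day 77. It becomes Day 75 to 81 for a last dose on Day 68 to 74, and Day 63 for a last dose on Day 56. The cost is a few lines of SAP wording and programming, with no new data.
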